Appendix L. Amendment 01 Changes

Summary of Amendment changes:

- Change of sample size
- Change of milestones

Section 4.0 Abstract

Previously read:

Study Design

RA patients, for whom adalimumab treatment has already been decided, will be recruited from within the clinical settings of each rheumatologist participating in the study.

Approximately 100 patients diagnosed with RA that meet the inclusion and exclusion criteria will be enrolled at approximately 9 sites in Korea.

Population

Subjects will be males and/or females who are attending a routine clinical visit and meet all of the inclusion criteria and none of the exclusion criteria. Approximately 100 patients diagnosed with RA will be recruited.

Study Size

Approximately 100 patients diagnosed with RA that meet the inclusion and exclusion criteria will be enrolled at approximately 9 sites in Korea. The sample size was calculated by assuming an alpha of 0.05 and a power of 0.80 in a two-sided test, resulting in 52 subjects required to recognize a statistically significant improvement in HAQ DI (-0.21). Given the importance of other secondary endpoints, an improvement of 9.9 ± 25 hours of work time lost requires 58 subjects, assuming an alpha of 0.05 and a power of 0.80 in a two-sided test. However, since it is expected that approximately half the study population may no longer be working due to their age, approximately twice this number (100 patients) will be required to achieve the required number of respondents. We have also assumed a drop-out rate of 13% (assuming between 10%-15%).

Milestones

Start of Data Collection: 19 Oct, 2015

End of Data Collection: 31 Jan, 2017

Study Progress Report: Not applicable

Interim Report: Not applicable

Registration in the EU PASS Register: Not Applicable

Final Report of Study Results: 31 Jul, 2017

Has been changed to read:

Study Design

RA patients, for whom adalimumab treatment has already been decided, will be recruited from within the clinical settings of each rheumatologist participating in the study. Approximately 89 patients diagnosed with RA that meet the inclusion and exclusion criteria will be enrolled at approximately 9 sites in Korea.

Population

Subjects will be males and/or females who are attending a routine clinical visit and meet all of the inclusion criteria and none of the exclusion criteria. Approximately 89 patients diagnosed with RA will be recruited.

Study Size

Approximately 89 patients diagnosed with RA that meet the inclusion and exclusion criteria will be enrolled at approximately 9 sites in Korea. The sample size was calculated by assuming an alpha of 0.05 and a power of 0.80 in a one-sided test, resulting in 36 subjects required to recognize a statistically significant improvement in HAQ DI (-0.21). Then, given the importance of other secondary endpoints, an improvement of 9.9 ± 25 hours of work time lost requires 40 subjects. However, since it is expected that approximately half the study population may no longer be working due to their age, we assume a 50% employment rate in the study population and a drop-out rate of 10%, eventually approximately 89 patients will be required to achieve the required number of respondents.

Milestones

Start of Data Collection: 19 Oct, 2015

End of Data Collection: 28 Feb, 2018

Study Progress Report: Not applicable

Interim Report: Not applicable

Registration in the EU PASS Register: Not Applicable

Final Report of Study Results: 31 Aug, 2018

Section 6.0 Milestones

Previously read:

Major study milestones and their planned dates are as follows:

Start of Data Collection (FPFV): 19 October 2015

End of Data Collection: 31 January 2017

Study Progress Report: Not Applicable

Interim Report: Not Applicable

Registration in the EU PAS register: Not Applicable

Final Report of Study Results: 31 July 2017

Has been changed to read:

Major study milestones and their planned dates are as follows:

Start of Data Collection (FPFV): 19 October 2015

End of Data Collection: 28 February 2018

Study Progress Report: Not Applicable

Interim Report: Not Applicable

Registration in the EU PAS register: Not Applicable

Final Report of Study Results: 31 August 2018

Section 9.1 Study Design

Previously read:

Approximately 100 patients diagnosed with RA that meet the inclusion and exclusion criteria will be enrolled at approximately 9 sites in Korea.

Has been changed to read:

Approximately 89 patients diagnosed with RA that meet the inclusion and exclusion criteria will be enrolled at approximately 9 sites in Korea.

Section 9.2 Setting

Previously read:

Overall, approximately 100 subjects with clinically diagnosed RA are planned to be enrolled in the study at up to 9 sites.

Has been changed to read:

Overall, approximately 89 subjects with clinically diagnosed RA are planned to be enrolled in the study at up to 9 sites.

Section 9.5 Study Size

Previously read:

Approximately 100 patients diagnosed with RA will be recruited. The planned sample size provides at least 95% power for detecting a statistically significant improvement in HAQ-DI (Δ HAQ-DI < 0) assuming a mean Δ HAQ-DI of -0.21 and a standard deviation of 0.5 (reference 11), at two-sided significance level of 0.05 and accounting for a 10% dropout rate. The sample size also provides at least 95% power for detecting a statistically significant clinically meaningful improvement in HAQ-DI (Δ HAQ-DI < -0.22) assuming a mean Δ HAQ-DI of -0.5 and a standard deviation of 0.7, at two-sided significance level of 0.05 and accounting for a 10% dropout rate. For the secondary endpoint WPAI, the sample size provides 63% power for detecting a statistically significant improvement in "hours of work lost" at two-sided significance level of 0.05 and accounting for a 10% dropout rate, assuming a mean change in "hours of work lost" of 10 and standard deviation of 30 and assuming a 55% employment rate in the study population.

Has been changed to read:

Approximately 89 patients diagnosed with RA will be recruited. The sample size was calculated by assuming an alpha of 0.05 and a power of 0.80 in a one-sided test, $Z(1-\alpha) = 1.645$ and $Z(1-\beta) = 0.842$. As to the primary variable, assuming a mean Δ HAQ-DI of -0.21 and a standard deviation (SD) of 0.5, according to the formula, 36 subjects are required. Then, given the importance of the secondary endpoint (WPAI), an improvement of 9.9 ± 25 hours of work time lost (mean=9.9, SD=25) requires 40 subjects. However, we assume a 50% employment rate in the study population and a drop-out rate of 10%, eventually approximately 89 patients will be required ($40/0.5/(1-0.1) = 89$).

AbbVie Inc. (AbbVie)
Post Marketing Observational Study
P15-777 Protocol

Real-World Outcome of Rheumatoid Arthritis Patients in Korea on Adalimumab
(ROCKA Study)

Amendment 01

Approved by:

	05 Mar 2018
	Date
	5 Mar 2018
	Date
	3 Mar 2018
	Date
	Apr 12th, 2018
	Date

**DOCUMENT HISTORY**

Version #	Issue Date	Author/Editor	Sections Changed	Change Summary
V0.2	2 Jan, 2018	[REDACTED]	Section	
 
1. Patient's impression of change in RA at weeks 12 and 24 after the initiation of adalimumab has been added in the Study Objectives and Statistical Analysis Section according to Taiwan protocol.
 
2. Disease status of RA (moderate, severe, missing) has been deleted in Table 2, since it's duplicated with DAS28 categorization.
 
3. Dosage of first adalimumab injection has been deleted in Table 2, since the DOSE should be 40MG for all adults.
 

V0.1	8 Aug, 2017	[REDACTED]	All	Initial Version

## 1. INTRODUCTION

### 1.1 Study Rationale and Background

Disability has been defined as impairments, activity limitations and participation restrictions due to personal and environmental factors (1). The concept of disability is one where a physical health condition or disease is evaluated in terms of its impact, difficulties, or limitations on a range of tasks, activities, or roles that are considered typical of everyday life. Examples of affected activities include basic aspects of daily living such as eating, bathing, dressing, household chores and meal preparation, or participation in society, or participation in work.

For public health purposes disability is becoming increasingly important as an outcome measure. Despite this, no data, within our knowledge, exist on the effectiveness of adalimumab on health-related QoL and work productivity in patients with Rheumatoid Arthritis (RA) in China, South Korea, and Taiwan.

Results from a study of the effect of adalimumab on Work Productivity and Activity Impairment (WPAI) scores and other Patient-Reported Outcomes (PROs) of work activity and well-being will be of interest to a variety of stakeholders in the healthcare system, including patients, healthcare practitioners and payers in China, South Korea and Taiwan.

Reimbursement in Taiwan and South Korea is strongly influenced by local “real - world” evidence of the intervention’s effects on outcomes and economic endpoints. The Chinese government has for some time been deeply concerned with an impending productivity decrease associated with ageing and chronic illnesses, including musculoskeletal disorders. These concerns have a large impact on their health financing and structuring policies. Therefore, having economic and health outcomes “real world evidence” (RWE) for the use of Humira (Adalimumab) in moderate RA patients from South Korea, Taiwan and China will be valuable to support the reimbursement / pricing maintenance and expansion in these countries.

In addition, the Bureau of National Health Insurance (BNHI) in Taiwan endorsed Dose Tapering and Withdraw (DT&W) guideline that was effective in Jan 2013. Under the DT&W policy, it indicated that when a patient with RA who is on Humira for more than 2 years, regardless of his/her disease state, will be tapered to 50% less dosage for 12 months and then to zero dosage after being tapered over one year. The government aims to implement DT&W policy to reduce the total health care spending

on the biologics. Although the policy was implemented since 2013, physicians are generally reluctant to dose tapering patients as well as patients. In this regard, it is acknowledged by both physician associations and patients associations that there is a real need to collect RWE to demonstrate the value of continued use of biologics to payers.

In Korea, Humira is reimbursed for both moderate and severe RA patients. However, the recent policy change in Korea indicated that the paradigm of using the ICER as the only value metric has been recently shifting toward considering other criteria such as patient reported outcomes, equity, innovation, and affordability. For example, the Korean government is in discussion with industry and academics to incorporate multi-criteria decision analysis (MCDA) such as including patient reported outcomes into HTA for new medical technologies and post launch product price management. In this regard, generating the RWE is critical for the price re-negotiation and protection with the national payer, under current reimbursement and pricing policies in South Korea.

In China, Humira is not listed on either provincial reimbursed drug list (PRDL) or national reimbursed drug list (NRDL), which means that patients have to pay for the use of biologics including Humira. Given the high costs of biologics, the use of biologics, including Humira in patients in RA is low in China. The average length of Humira use for patients with RA in China is only 3 months.

On August 30th, 2012, National Development and Reform Commission (NDRC), Ministry of Health (MOH) and other four ministries and commissions of China issued “Guidance about implementation of urban and rural residents’ critical disease insurance (CDI) system”. The CDI system aims to expand the coverage of the country’s health care insurance system to include the treatment of critical illness, aiming to relieve urban and rural families of the heavy burden of catastrophic medical spending. By the end of August 2013, 94 regions across 23 provinces had piloted the critical illness cover system and seven provinces had fully implemented the system, benefiting 210 million people.

In Jan 2015, Humira was listed on the CDI in Qingdao. Patients with RA who are covered by CDI are reimbursed for 70 percent of the total costs. Given CDI is a new system in China, the Qingdao officials encourage companies to collect the RWE associated with the use of Humira to further demonstrate the value of Humira to patients. The result will assist decision makers to evaluate the CDI from a broader perspective and to determine the value of continuing the program.

In addition, generating RWE related with the use of Humira in patients with RA will be extremely valuable for application of Humira on the CDI list in other provinces in China. The successful applications in other provinces will ensure more patients with RA in China will be able to access the Humira.

The objective of this non-interventional, observational study is to assess the effect of adalimumab on health-related QoL, work productivity, and healthcare resource utilization (HCRU) in patients with RA in China, South Korea, and Taiwan.

## **2. OBJECTIVES**

The objective of this study is to assess the effect of adalimumab on health and disability outcomes in patients with the immune-mediated inflammatory diseases of rheumatoid arthritis. The effect of adalimumab on health and disability outcomes in these patients will be assessed by the primary outcome measure which is the change in Health Assessment Questionnaire Disability Index (HAQ DI) score at 24 weeks after the initiation of adalimumab (i.e. baseline). The HAQ DI is selected as the primary endpoint as it is commonly used to assess improvements in physical function in RA clinical trials and recommended by the US Food and Drug Administration (FDA) guidance on RA treatment development (3, 4). In addition, the HAQ DI has been utilized as a predictor variable in investigations of productivity (5). The HAQ DI has been demonstrated to be significantly correlated with work-related measures such as work capacity, household work performance, work task performance, and work disability (6-9). In addition, the effect of adalimumab will also be assessed by the secondary outcome measures which are changes to the WPAI, EuroQol 5 dimension 3 level (EQ-5D-3L) index, and Short Form 36-Item Health Survey (SF-36) domain scores at 12 and 24 weeks after the initiation of adalimumab in RA.

### **2.1 Primary Objectives**

- To describe the change in HAQ DI score at 24 weeks after the initiation of adalimumab (i.e. baseline), in those patients continuing on adalimumab (responder population). This change will be summarized as the mean and 95% confidence interval and will be tested with a paired t-test.

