9.7.2 Analyzable population

All subjects who received at least one dose of adalimumab during the study will be included. The main analysis will be conducted on the pooled population, where appropriate, with each individual country analyzed separately as supportive data.

9.7.3**Planned Methods of Statistical Analysis**

All statistical tests will be two-tailed with a significance level of 0.05. Descriptive statistics will be provided. Descriptive analysis will be conducted on all key parameters and presented as mean, standard deviation, minimum, maximum, and median when continuous and as “n” and percent when categorical. Change from adalimumab initiation to 24 weeks will be calculated and evaluated for significant improvements using paired t-tests / ANOVA for parametric and Wilcoxon signed-rank for non-parametric data. Analysis will be also be conducted by severity level (moderate vs severe), disease duration quartile (to compare to prior work) and up to two (2) other subgroups. Cochran-Armitage test of trends or other similar methods may be used to compare categories of subjects.

9.7.4**Primary Endpoint Analysis**

The primary endpoint variable will be the change in HAQ DI score at 24 weeks after the initiation of adalimumab (observed population).

The objective of the primary endpoint analysis will be to demonstrate that treatment with adalimumab improves functioning as measured by the HAQ DI in subjects with RA following treatment initiation. This change will be summarized as the mean and 95% confidence interval and will be tested with a paired t-test.

The primary analysis will be summarized as the mean and 95% confidence interval and will be tested with a paired t-test without adjusting for baseline disease severity. For sensitivity analysis, the mean change in HAQ DI at Week 24 will be analyzed using ANOVA adjusting for baseline disease severity.

9.7.5**Secondary Endpoint Analysis**

The main secondary endpoint variable will be the change in HAQ DI at 12 weeks after the initiation of adalimumab.

The objective of endpoint analysis will be to demonstrate that treatment with adalimumab improves functioning as measured by HAQ DI in subjects with RA compared to baseline.

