The main secondary analysis will be summarized as the mean and 95% confidence interval and will be tested with a paired t-test without adjusting for baseline disease severity. For sensitivity analysis, the mean change in HAQ DI at Week 12 will be analyzed using ANOVA adjusting for baseline disease severity.

Other secondary analysis include:

- Change in other patient reported outcomes (SF-36 domain scales, EQ-5D Index, WPAI total lost productivity) at weeks 12 and 24 after the initiation of adalimumab, in those patients continuing on adalimumab (observed population). These changes will be summarized as the means and 95% confidence intervals and will be tested with paired t-tests.
- Number and percent of patients achieving a clinically meaningful improvement on the HAQ DI, as defined by a -0.22 point improvement or greater, at weeks 12 and 24 after the initiation of adalimumab (observed population).

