### **2.2 Secondary Objectives**

- To describe the change in other patient reported outcomes (SF-36 domain scales, EQ-5D-3L index, WPAI total lost productivity) at weeks 12 and 24 after the initiation of adalimumab, in those patients continuing on adalimumab (responder

population). These changes will be summarized as the means and 95% confidence intervals and will be tested with paired t-tests.

- To describe the change in patient satisfaction questions at weeks 12 and 24 after the initiation of adalimumab, in those patients continuing on adalimumab (responder population). These changes will be summarized as number and percentage of each response and compared with Wilcoxon signed rank test. Satisfaction will also be dichotomized and analyzed over time with Cochran-Armitage test for trends.
- To summarize the number and percent of patients achieving a clinically meaningful improvement on the HAQ DI, as defined by a -0.22 point improvement or greater, at weeks 12 and 24 after the initiation of adalimumab, in those patients continuing on adalimumab (responder population).

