### 2.3 Additional Secondary Objectives

- To describe the change in HAQ DI score at 24 weeks after the initiation of adalimumab, in those patients continuing on adalimumab (responder population), compared with those patients not continuing on adalimumab (non-responders). The mean changes in these two groups will be compared using an independent t-test.
- Patient's impression of change in RA at weeks 12 and 24 after the initiation of adalimumab, in those patients continuing on adalimumab (as observed population). Each response will be summarized as number and percentage.
- To summarize the healthcare resource utilization using number and percentage within each category (number of consultations, number of procedures received, number of surgeries, number of hospitalizations and length of stay, number and type of concomitant medications)
- To analyze the associations between disease severity and PROs (HAQ DI, SF-36 domain scales, EQ-5D-3L index, WPAI total lost productivity)
- To analyze the associations between change in disease severity and change in PROs (HAQ DI, SF-36 domain scales, EQ-5D-3L index, WPAI total lost productivity)

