## 5.3 Analysis Plan for Primary Objectives

The objective of the primary endpoint analysis will be to demonstrate that treatment with adalimumab improves functioning as measured by the HAQ DI score in subjects with RA following treatment initiation (i.e. baseline).

- The changes in HAQ DI score at 12 and 24 weeks after the initiation of adalimumab will be presented (Excel Table 3.1); these changes will be summarized as the mean, SD, minimum, maximum, median, 95% confidence interval; as well as the number and percent of patients achieving a clinically meaningful improvement on the HAQ DI, as defined by a -0.22 point improvement or greater. In addition, the mean change will be tested with a paired t-test without adjusting for baseline disease severity, shown by p-value1; for sensitivity analysis, the mean change will be analyzed using ANOVA adjusting for baseline disease severity, shown by p-value2 in the table.
- The change in HAQ DI score at 24 weeks after the initiation of adalimumab (mean, SD, minimum, maximum, median, 95% confidence interval), in those patients continuing on adalimumab (responder population) will be compared with those patients not continuing on adalimumab (non-responders). The mean

changes in these two groups will be compared using an independent t-test with p-value listed in the table (Excel Table 3.2).

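### Patients who stop adalimumab drop out of the primary HAQ DI mean and the -0.22 achiever rate with no missing-data sensitivity analysis, and neither document says which HAQ value represents them in Table 3.2

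*SAP*

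**What the plan says.** **Who is analysed.** Protocol 9.7.2 states: "All subjects who received at least one dose of adalimumab during the study will be included". Protocol 9.7.5 then describes its other patient-reported outcome changes "in those patients continuing on adalimumab (observed population"), which shows that the observed population means continuers; 9.7.4 uses the same label for the primary endpoint. SAP 2.1 sets the primary change "in those patients continuing on adalimumab (responder population"). SAP 2.2 applies the same restriction to the "number and percent of patients achieving a clinically meaningful improvement on the HAQ DI, as defined by a -0.22 point improvement or greater". SAP 2.3 uses a third label for the same group, "in those patients continuing on adalimumab (as observed population").

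**Missing data.** Protocol 9.7.9 and SAP 3.5.5 say that efficacy is not assessed after adalimumab is stopped and that only questionnaire items are imputed (the SAP adds a missing day in a date). SAP 3.5.5 says the missing data cannot be taken as MCAR or MAR, rejects multiple imputation for that reason, and uses available data. Both sections foresee an analysis of the share of patients still on treatment at Week 24, and the SAP will report counts of missing data.

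**Sensitivity analysis.** SAP 5.3, in line with Protocol 9.7.4, names one: "for sensitivity analysis, the mean change will be analyzed using ANOVA adjusting for baseline disease severity".

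**Continuers against stoppers.** Protocol 9.7.6, SAP 2.3 and SAP 5.3 call for the Week 24 change in continuers, which "will be compared with those patients not continuing on adalimumab (non-responders"). SAP 2.3 gives the method: "The mean changes in these two groups will be compared using an independent t-test". Protocol Table 1 (9.1.1) schedules a HAQ at early termination. Protocol 17.0 counts being switched off adalimumab as drop-out and ends data collection there.

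**The concern.** Protocol 9.7.4 and SAP 5.3 set out to demonstrate that adalimumab improves functioning. The reported mean and achiever rate describe patients still on treatment at Week 24. The reasons for stopping listed on the clinician's form in Appendix K include disease progression and adverse events, so loss may be related to outcome. The SAP's own statement about the missing-data mechanism points the same way: if data are neither MCAR nor MAR, an available-case mean can also be biased for the patients who started treatment. An ANOVA on the same patients cannot show by how much. The persistence proportion and the missing counts show how many are lost, not how far the mean could move.

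Table 3.2 is a second gap. A stopper may have a Week 12 value, an early-termination value, both or neither. None of these need be at Week 24, and the documents do not say which enters the t-test. Two programmers could build different comparison groups. The list of tables in SAP section 6 calls the groups responders and non-responders, although they are defined by staying on treatment.

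**Working it through.** **1. The plan's own figure.** Protocol 9.5 gives a mean change of -0.21, SD 0.5, one-sided alpha 0.05 and power 0.80. Then n = (0.5 × (1.645 + 0.842)/0.21)² = 35.06, so 36. For work time lost, n = (25 × 2.487/9.9)² = 39.44, so 40, and 40/0.5/0.9 = 88.9, so 89. The stated 36, 40 and 89 all reproduce, and the sample size is not in dispute here.

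**2. Assumptions not in the documents.** Every drop-out is a stopper (an upper bound at the 10% of Protocol 9.5). The planning values -0.21 and SD 0.5 hold in continuers. Stoppers have mean change x with SD 0.5. Changes are normal. Of 89 patients, 80 continue and 9 stop.

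**3. Mean change.** Continuers alone: -0.21, with 95% CI half-width 1.990 × 0.5/√80 = 0.111 and two-sided power about 96%. All dosed: 0.9 × (-0.21) + 0.1x.

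| Stopper mean x | All-dosed mean | Against -0.21 |
|---|---|---|
| -0.42 | -0.231 | 10% larger |
| -0.21 | -0.210 | none |
| 0 | -0.189 | 10% smaller |
| +0.25 | -0.164 | 22% smaller |

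**4. Tipping point.** The mixture SD is √(0.25 + 0.09(x + 0.21)²). Two-sided significance at n = 89 is lost when mean/(SD/√89) = -1.987. At x = 0.69 the mean is -0.120, the SD 0.568 and t = -1.992, so the tipping point is about +0.69. Using the actual counts, it falls to about +0.44 with 13 stoppers (about 15%), +0.28 with 18 (20%) and +0.12 with 27 (30%).

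**5. Achiever rate.** In continuers, Φ((-0.22 + 0.21)/0.5) = Φ(-0.02) = 0.492, or about 39 of 80 (49%). Whatever the stoppers' outcomes, the all-dosed rate lies between 39/89 = 44% (none achieved) and 48/89 = 54% (all achieved).

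**6. Table 3.2.** If all 9 stoppers have a usable HAQ value, 80 against 9 with SD 0.5 has 22% power for a 0.21 difference. The CI half-width is 1.988 × 0.5 × √(1/80 + 1/9) = 0.349, and 80% power needs a difference of about 0.50. With values for only 3 of the 9 (an assumption), power is 11% and the half-width 0.585.

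**The case against.** The strongest reply is that the target is declared: SAP 2.1 sets out to describe change in continuers, in a single-arm observational study, and Protocol 9.9 admits possible missing data. On the illustrated figures the effect is modest: a shift of 0.046 against a CI half-width of 0.111, and an achiever rate moving from 49% to 44% against a half-width of about 11 points (1.96 × √(0.4875 × 0.5125/80) = 0.110). The all-dosed achiever rate could also be worked out by a reader from the achiever count and the number treated. All of this stands and limits the weight of the point. It does not supply what is missing for the mean, which cannot be recovered from counts.

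A separate table-shell workbook, cited in SAP 5.1 and section 6, might hold a rule for Table 3.2. That is possible, but such a rule belongs in the SAP text.

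Several stronger readings are tempting and are not supported:

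- *Protocol 9.7.2 and SAP 2.1 define rival primary populations.* SAP 5.3 does not repeat the continuer restriction for Table 3.1, and SAP 5.1 can be read as allowing an all-patient percentage. But with no assessment after stopping and no imputation, either wording selects nearly the same patients for the Week 24 mean. The wording is loose; the analysed set hardly changes.
- *HAQ is not collected from stoppers because the patient form in Appendix K lacks it.* The routine follow-up resource-use form in Appendix J lacks it too, and HAQ is plainly scheduled at those visits. Table 1 schedules it at early termination, and Protocol 17.0 can be read as ending collection after that visit.
- *The SAP claims that available-case analysis avoids bias.* SAP 3.5.5 says only that multiple imputation would introduce it.
- *The t-test must go because its power is low.* It is specified in Protocol 9.7.6, and dropping it would be a preference.

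**Conclusion.** The point holds as a worthwhile, inexpensive improvement. The primary mean and the -0.22 rate describe continuers. The SAP's own view of the missing data implies that these estimates may not carry over to all who start treatment, and no planned analysis shows how far the mean could differ. Table 3.2 lacks a rule for the stopper's HAQ value and its timing.

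The size and direction of the bias are unknown, and every stopper mean used here is an assumption. What is at stake is the size of the reported effect. A reader might infer that the primary result is in danger, but at the planned 10% drop-out stoppers would have to worsen by about 0.69 on average before two-sided significance is lost. That margin narrows only if stopping is well above plan.

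**What to change.** 1. Keep the continuer analysis. Beside it, report the -0.22 achiever rate with all dosed patients who have a baseline HAQ as denominator, counting stopped or missing as not achieved.
2. Add a delta (tipping-point) sensitivity analysis of the Week 24 mean change: impute missing changes from the continuers' distribution given baseline HAQ, shifted by delta from -0.2 to +0.5 and on to the value at which two-sided p reaches 0.05. State in SAP 3.5.5 that available-case results may also be biased when data are not MCAR or MAR.
3. Reconcile Protocol Table 1, 9.7.9 and 17.0 with SAP 3.5.5 and 5.3 on which HAQ value represents a stopper. Label Table 3.2 as change to last available HAQ, show the assessment time, and name the groups continuers and discontinuers. Treat any p-value there as descriptive; the t-test need not be deleted.

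The cost is wording in both documents and two additional results to tabulate. Items 1 and 2 need no new data, and item 3 uses whatever HAQ values exist. The drawback is that the all-dosed achiever rate is conservative and will look less favourable.
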